8.5.3 CSF Sample (only for Participants who are Enrolled by CSF Amyloid Assessment)

Cerebrospinal fluid will be obtained from participants who choose to provide CSF samples during screening (CSF-enrolled participants) for confirmation of $A\beta$ and tau levels for eligibility purposes.

Cerebrospinal fluid will be collected via LP by an individual who meets all local requirements and is proficient in the procedure. Cerebrospinal fluid sampling and post-LP care will be performed in accordance with local practice. All CSF sampling should be performed in the morning (between 8:00 a.m. and noon) to minimize potential diurnal variability of CSF biomarkers.

Approximately 12 mL of CSF will be collected at screening. The sample will be divided into aliquots onsite and used for the following:

- Biomarker analysis, including, but not limited to: $A\beta_{1-42}$, $A\beta_{1-40}$, tTau, pTau, and NfL
- Measurement of gantenerumab levels in the CSF
- Samples may also be used to support the development of biomarker assays for diagnostic use

8.5.4 Brain Magnetic Resonance Imaging

Magnetic resonance imaging should be performed with use of 1.5-T or 3.0-T scanners. Whenever possible, the same scanner should be used for an individual participant for the entire duration of the study. Magnetic resonance imaging will be conducted at screening to (1) determine whether the exclusion criteria are met (e.g., number of microhemorrhages or presence of mass lesions), (2) serve as a baseline measure of (regional) brain volumes and (3) serve as baseline information for the PET assessments (where applicable). In addition, structural MRI (to assess whole-brain and regional brain atrophy), and optional imaging, including functional resting-state MRI (rs-fMRI), dMRI, and ASL-MRI, will be performed at multiple timepoints to determine potential treatment effects on MRI outcome measures (for the schedule of activities, see Section 1.3).

Magnetic resonance imaging will also be used during the entire study to monitor safety (e.g., occurrence of ARIA-E or ARIA-H). Additional unscheduled MRI scans may be performed to better understand relevant CNS adverse events (such as increased confusion) occurring in the context of ARIA or to follow-up a sign that emerges at a scheduled scan. Contrast agent may be used in such a case of follow-up MRI scans if clinically indicated and administration of contrast agent is considered safe for the participant according to local standards. If a contrast agent is used, the participant's renal function must be checked according to the local standards to ensure that contrast administration is safe.

Magnetic resonance imaging should be performed before or at least 3 days after CSF sampling (i.e., LP), unless an earlier MRI scan is clinically warranted.

Magnetic resonance imaging scans may include all or some of the following sequences:

Core Sequences:

- 3D T₁-weighted
- T₂*-weighted

- T₂-weighted
- T₂-FLAIR
- DWI

Optional Sequences (subset of sites/subjects depends on the scanner specification):

- BOLD rs-fMRI and related fieldmap: optional and if available (to assess resting-state functional connectivity at investigative sites having the required software and sequences)
- dMRI and related fieldmap: optional and if available (to assess fiber tract integrity)
- ASL-MRI and related fieldmap: optional and if available (to assess CBF)

All sequences (except rs-fMRI, dMRI and ASL-MRI) will be used to assess MRI safety and inclusion/exclusion criteria. Additional sequences may be obtained if clinically warranted.

Magnetic resonance imaging scans will be reviewed by a central MRI core laboratory, which will perform both, the clinical reads and assessment of MRI outcome measures. Magnetic resonance imaging scans should preferably be transferred to the central MRI core laboratory electronically. Magnetic resonance imaging results must be made available to investigators before dosing can proceed (see Section 8.2.7 for additional details on MRI safety management).

Magnetic resonance imaging facility qualification and scan quality control will be performed by the central MRI core laboratory.

Additional MRI instructions regarding the specific imaging sequences, acquisition times, procedures for MRI scan acquisition and transmittal to the central reading facility can be found in the MRI Manual and Imaging Review Charter.

8.6 GENETICS

See Section 8.5.2 for information on clinical genotyping.

8.7 BIOMARKER ASSESSMENTS

See Section 8.5 for more information on plasma biomarker, clinical genotyping, and CSF assessments.

The following biomarker samples will be collected, as applicable, from participants at all sites:

- Clinical Genotyping Samples
- CSF Sample – only for participants who are enrolled by CSF amyloid assessment
- Plasma Biomarker Samples

Biomarker samples collected at participating sites and biomarker samples requiring separate consent are described in Section 8.11.

Plasma biomarker samples and CSF samples collected at screening, including those collected from individuals who do not enroll in the study, may be used for exploratory research and/or development of disease-related tests or tools.

Biomarker samples will be collected according to the schedule of assessment outlined in Section 1.3. Biomarker samples will be sent to one or several central laboratories or to the Sponsor or a designee. Instructions for the collection and handling of biomarker samples, including sampling procedures, storage conditions, and shipment instructions, are provided in the laboratory manual.

Unless the participant gives specific consent for his or her leftover samples to be stored for optional exploratory research (see Section 8.11.5) biomarker samples will be destroyed no later than 5 years after the final Clinical Study Report has been completed.

Given the complexity and exploratory nature of exploratory biomarker analyses, data derived from these analyses will generally not be provided to study investigators or participants unless required by law. The aggregate results of any conducted research will be available in accordance with the effective Sponsor policy on study data publication. Results of biomarker analyses may be reported outside of the CSR.

8.8 IMMUNOGENICITY ASSESSMENTS

Antibodies to gantenerumab will be evaluated in plasma samples collected from all participants according to the schedule of activities (see Section 1.3). Additionally, plasma samples should also be collected at the final visit from participants who discontinued study treatment or were withdrawn from the study. These samples will be tested by the Sponsor or Sponsor's designee.

Plasma samples will be screened for antibodies binding to gantenerumab and the titer of confirmed positive samples will be reported.

All samples collected for detection of antibodies to study treatment will also be evaluated for gantenerumab plasma concentration to enable interpretation of the antibody data. Samples may be stored for a maximum of 5 years (or according to local regulations) after the final Clinical Study report has been completed at a facility selected by the Sponsor to enable further analysis of immune responses to gantenerumab.

Remaining volumes from these samples may also be used for further characterization of potential immune responses and for any gantenerumab-related exploratory analyses or assay development/validation experiments.

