Protocol WN42444 has been amended to address a health authority (HA) requirement to include a coronavirus disease 2019 (COVID-19) vaccination risk assessment, clarify magnetic resonance imaging (MRI) monitoring requirements, the requirements for starting the post-progression dose escalation period, the assessment schedule related to the post-progression escalation period, the process of rescreening, and to add plasma samples as specified below. Substantive changes to the protocol, along with a rationale for each change, are summarized below.

- Sections 2.3 and 6.8.1 have been updated to address a HA requirement to include a COVID-19 vaccination risk assessment
- Section 8.2.7 has been updated to clarify the MRI safety monitoring schedule for each study period (initial dose escalation, maintenance dosing, and post-progression dose escalation periods) and dosing schedule (every week [Q1W], every 2 weeks [Q2W], every 4 weeks [Q4W])
- Table A3-1 has been updated to clarify timing of MRIs related to amyloid-related imaging abnormality (ARIA) management for each study period and dosing schedule
- Footnotes have been added to Tables 2, 3, 5 and 6 to clarify the assessment schedule during and following the post-progression dose escalation
- Text has been updated to clarify that, before a participant enters the post-progression dose escalation period based on having clinically progressed, they need to be on target dose; it has also been clarified that, in order to conclude on clinical progression, the change in diagnostic classification must be confirmed on a second visit, approximately 6 months later so that the diagnosis can be considered stable
- Pharmacokinetic samples at Week 131 and Week 183 have been added in Table 2 and Table 5 because they are needed for the valid assessment of anti-drug antibodies (ADAs) at these timepoints
- Tables 1–6 and A24-1 have been updated to clarify prothrombin time collection timepoints
- The process for rescreening has been clarified

Additional minor changes have been made to improve clarity and consistency. Substantive new information appears in *italics*. This amendment represents cumulative changes to the original protocol.

TABLE OF CONTENTS

1.	PROTOCOL SUMMARY.....	13
1.1	Synopsis	13
1.2	Study Design	19
1.3	Schedule of Activities	20
2.	INTRODUCTION	48
2.1	Study Rationale	48
2.2	Background	48
2.3	Benefit–Risk Assessment.....	50
3.	OBJECTIVES AND ENDPOINTS AND ESTIMANDS	52
4.	STUDY DESIGN	55
4.1	Overall Design	55

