- ⁱ Cerebrospinal fluid collection must be performed in the morning (between 8:00 a.m. and noon) to minimize potential diurnal variation of CSF parameters and should be performed prior to dosing. For Early Termination visits, CSF sampling should only be obtained if the last CSF sampling was > 6 months earlier.
- ^j Every 4 weeks, except when there is an in-clinic visit, the investigator or an appointed qualified study staff member will have a telephone conversation with the participant and study partner to elicit, in a non-leading way, information on medication errors, adverse events, and changes to concomitant medications that may have occurred in the home setting. Therefore, there will be contact between the study staff and the participant/study partner at least every 4 weeks. The study staff is encouraged to have more frequent calls with a particular participant/study partner if considered appropriate by the investigator. In addition, the participant and study partner must be instructed to contact the investigator and seek approval for continued study drug dosing in the home setting in case of onset of any new symptoms or symptom worsening, new or changed concomitant medications, or medication errors.

Table 2 Schedule of Activities: Week 38 to End of Study; 255 mg Q1W

Assessment/ Procedure (week)	Maintenance Dosing from Week 38 to Week 210													Final Safety and Efficacy Assessment	Follow-up Safety Assessment	Early Term Visit (2 weeks after last study drug dose)	Unsch Visit ^a
	38 to 52	53	54 to 78	79	80 to 104	105	106 to 130	131	132 to 156	157	158 to 182	183	184 to 210	Week 211	Week 227 or 15 weeks after Early Term Visit		
Dose number	14 to 28	29	30 to 54	55	56 to 80	81	82 to 106	107	108 to 132	133	134 to 158	159	160 to 186				
Dose level (mg)	255	255	255	255	255	255	255	255	255	255	255	255	255				
Study Drug Administration	C/ CS/ H/ MN	C/ CS	C/ CS/ H/ MN	C/ CS	C/ CS/ H/ MN	C/ CS	C/ CS/ H/ MN	C/ CS	C/ CS/ H/ MN	C/ CS	C/ CS/ H/ MN	C/ CS	C/ CS/ H/ MN				
12-lead ECG		x ^B		x ^B		x ^B		x ^B		x ^B		x ^B		x	x	x	x
PK plasma sample ^b		x ^B		x ^B		x ^B		x ^B		x ^B		x ^B		x		x	x
Plasma biomarker sample ^b		x ^B		x ^B		x ^B				x ^B				x	x	x	x
ADA plasma sample ^b		x ^B		x ^B		x ^B		x ^B		x ^B		x ^B		x		x	x
Serum chemistry and hematology		x ^B		x ^B		x ^B		x ^B		x ^B		x ^B		x	x	x	x
Metabolic tests, CRP, and PT ^c		x ^B				x ^B				x ^B				x	x	x	x
Complete physical examination (Includes neurologic systems)		x ^B				x ^B				x ^B				x	x	x	x

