ADA = anti-drug antibody; AD-CGI-S = Clinician Global Impression of Cognitive Function; AD-PGI-S = Participant Global Impression of Cognitive Function; AD-SPGI-S = Study Partner Global Impression of Cognitive Function; A-IADL-Q-SV = Amsterdam Instrumental Activities of Daily Living Questionnaire Short Version; ARIA-E = amyloid-related imaging abnormalities – edema/effusion; ARIA-H = amyloid-related imaging abnormalities – hemosiderin deposition; C = in-clinic administration by study staff; CDR = Clinical Dementia Rating; CFIa = Cognitive Function Instrument acute; CRP = C-reactive protein; C-SSRS = Columbia-Suicide Severity Rating Scale; CS = supervised in-clinic administration, where applicable; CSF = cerebrospinal fluid; DCF = Diagnostic Classification Form; Early Term = Early Termination; EQ-5D-5L = EuroQol 5-Dimension 5-Level Questionnaire; GDS-30 = Geriatric Depression Scale; H = visit appropriate for home administration by participant or

Table 2 Schedule of Activities: Week 38 to End of Study; 255 mg Q1W (cont.)

study partner, where applicable; MN = visit appropriate for home administration by *mobile* nursing professional, where applicable; MRI = magnetic resonance imaging; PACC-5 = Preclinical Alzheimer's Cognitive Composite-5; PET = positron emission tomography; PK = pharmacokinetic; Q1W = every 1 week; Unsch = unscheduled; Wk = week.

x^B = before study drug administration; visits may be split over 2 consecutive days.

As per [Table 1](#), participants reach the target dose at Week 37 after which they will continue with the Q1W dosing frequency. Subsequently, the next dose after Week 37 is given at Week 38, and last dose is given at Week 210 during maintenance dosing.

Participants should be observed for at least 2 hours after dosing at Week 1, Week 5, Week 9 and Week 13; the observation time may be reduced to at least 1 hour following all other administrations.

- ^a Scope of the unscheduled visit should include all efficacy assessments if they were missed at the preceding, regularly scheduled efficacy assessments visit. Safety assessments, including physical examinations, must also be included if they were missed at the preceding, regularly scheduled safety assessments visit or as clinically indicated. Unscheduled visits related to the occurrence of ARIA-E or ARIA-H are to follow the PK and plasma biomarker sampling rules as detailed below.
- ^b Visits, that include PK, ADA and plasma biomarker sampling must take place in-clinic.

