ADA = anti-drug antibody; AD-CGI-S = Clinician Global Impression of Cognitive Function; AD-PGI-S = Participant Global Impression of Cognitive Function; AD-SPGI-S = Study Partner Global Impression of Cognitive Function; A-IADL-Q-SV = Amsterdam Instrumental Activities of Daily Living Questionnaire Short Version; ARIA-E = amyloid-related imaging abnormalities – edema/effusion; ARIA-H = amyloid-related imaging abnormalities – hemosiderin deposition; C = in-clinic administration by study staff; CDR = Clinical Dementia Rating; CFla = Cognitive Function Instrument acute; C-SSRS = Columbia-Suicide Severity Rating Scale; CS = supervised in-clinic administration, where applicable; CSF = cerebrospinal fluid; DCF = Diagnostic Classification Form; Early Term = Early Termination; EQ-5D-5L = EuroQol 5-Dimension 5-Level Questionnaire; GDS-30 = Geriatric Depression Scale; H = visit appropriate for home administration by participant or study partner, where applicable; MN = visit appropriate for home administration by *mobile* nursing professional, where applicable; MRI = magnetic resonance imaging; PACC-5 = Preclinical Alzheimer’s Cognitive Composite-5; PET = positron emission tomography; PK = pharmacokinetic; Q2W = every 2 weeks; Unsch = unscheduled; Wk = week.

Table 5 Schedule of Activities: Week 38 to End of Treatment Period (Week 211); 510 mg Q2W (cont.)

x^B = before study drug administration; visits may be split over 2 consecutive days.

As per Table 4, participants reach the target dose at Week 37 after which they continue with the Q2W dosing frequency. Subsequently, the next dose after Week 37 is given at Week 39, and last dose is given at Week 209 during maintenance dosing.

Participants should be observed for at least 2 hours after dosing at Week 1, Week 5, Week 9 and Week 13; the observation time may be reduced to at least 1 hour following all other administrations.

- ^a Scope of the unscheduled visit should include all efficacy assessments if they were missed at the preceding, regularly scheduled efficacy assessments visit. Safety assessments, including physical examinations, must also be included if they were missed at the preceding, regularly scheduled safety assessments visit or as clinically indicated. Unscheduled visits related to the occurrence of ARIA-E or ARIA-H are to follow the PK and plasma biomarker sampling rules as detailed below.
- ^b Visits, including PK, ADA and plasma biomarker sampling must take place in-clinic.

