Participants who discontinue from the study treatment for any reason should be encouraged to continue with all remaining assessments until the end of the study. However, participants who are unwilling to return to the clinic will be asked to complete the Early Termination and safety follow-up visits within 2 weeks and 17 weeks, respectively from the final dose of study drug.

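### Completers and early terminators give their last scheduled ADA and PK samples 1–2 weeks after the last dose; the follow-up visit at 17–18 weeks draws blood but takes neither

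*Combined protocol and SAP*

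**What the plan says.** **Schedule.** In Table 2 (Q1W) and Table 5 (Q2W), Section 1.3, the PK and ADA rows are marked at Weeks 53, 79, 105, 131, 157, 183 and 211, at Early Termination and at unscheduled visits. Both rows are blank in the follow-up safety column, which is headed "Week 227 or 15 weeks after Early Term Visit". The same column is marked for serum chemistry and hematology, for metabolic tests, CRP and PT, and for a plasma biomarker sample. Table A24–1 confirms the safety laboratory tests at that visit.

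**Last dose.** For Q1W, the notes to Table 2 state that the "last dose is given at Week 210 during maintenance dosing". For Q2W, the notes to Table 5 state that the "last dose is given at Week 209 during maintenance dosing". The Early Termination visit is 2 weeks after the last dose.

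**Discontinuers.** Section 8.8 says: "Additionally, plasma samples should also be collected at the final visit from participants who discontinued study treatment or were withdrawn from the study". The term final visit is not defined. Section 7.1 asks participants who stop treatment and are unwilling to return to "complete the Early Termination and safety follow-up visits within 2 weeks and 17 weeks, respectively from the final dose of study drug".

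**Use of the data.** Presence of ADA relative to baseline is a secondary safety endpoint (Table 7). Section 9.4.5.4 summarizes post-baseline incidence in exposed participants. A participant negative or missing at baseline is ADA-negative if every post-baseline sample is negative. Section 8.8 has each ADA sample also assayed for drug concentration, so that the antibody result can be interpreted. The amendment rationale added PK samples at Weeks 131 and 183 "because they are needed for the valid assessment of anti-drug antibodies (ADAs) at these timepoints".

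**The concern.** By pairing each ADA sample with a concentration, the protocol treats circulating drug as relevant to reading the ADA result. The baseline sample is drug-free. For someone who stays on treatment to Week 210 or 209, every later scheduled sample is taken with drug present, and the last is about one maintenance dosing interval after the final dose. An antibody response that the assay cannot see at trough, or one that emerges once dosing stops, would not be picked up. Under the Section 9.4.5.4 rule that participant would count as ADA-negative.

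Adverse events are collected for 17 weeks after the final dose (Section 8.3.1), and Appendix 3 (A3–3) names ADA as a possible cause of allergic reactions. Scheduled immunogenicity sampling stops 15–16 weeks before that window closes. The plasma biomarker sample taken at the follow-up visit also has no paired concentration, so it cannot be related to residual exposure.

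**Working it through.** **1. The plan's own interval.** The protocol puts the safety follow-up 17 weeks after the final dose (Sections 4.1.4, 7.1 and 7.2). From the table columns:

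| Group | Last dose | Last scheduled ADA/PK | Interval | Follow-up visit | Interval from last dose |
|---|---|---|---|---|---|
| Q1W completers | Week 210 | Week 211 | 211 − 210 = 1 week | Week 227 | 227 − 210 = 17 weeks |
| Q2W completers | Week 209 | Week 211 | 211 − 209 = 2 weeks | Week 227 | 227 − 209 = 18 weeks |
| Early terminators | – | Early Termination | 2 weeks | Early Termination + 15 weeks | 2 + 15 = 17 weeks |

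The stated 17 weeks is reproduced for Q1W completers and early terminators; Q2W completers come out one week later. The last-dose weeks agree with the tabulated dose numbers: 14 + (210 − 38) = 186 for Q1W and 11 + (209 − 39)/2 = 96 for Q2W.

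**2. Drug remaining (assumption).** No half-life is stated. I assume first-order decline with a half-life h of 2 to 5 weeks. The share of the last-dose concentration left after w weeks is 2^(−w/h).

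| h (weeks) | 1 week | 2 weeks | 17 weeks | 18 weeks |
|---|---|---|---|---|
| 2 | 71% | 50% | 0.3% | 0.2% |
| 3 | 79% | 63% | 2.0% | 1.6% |
| 4 | 84% | 71% | 5.3% | 4.4% |
| 5 | 87% | 76% | 9.5% | 8.3% |

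The contrast between the last scheduled sample and the follow-up visit holds across the range. At the longer half-lives some drug remains at 17–18 weeks, so the visit comes after a long drug-free interval but is not necessarily after washout.

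**3. Earlier low-concentration sample.** Tables 1 and 4 schedule predose ADA and PK at Week 13, four weeks after the third 120 mg Q4W dose. With r = 2^(−1/h), and assuming dose-proportional superposition:

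- Week 13: 120 × (r⁴ + r⁸ + r¹²). For h = 2 this is 120 × 0.328 = 39; for h = 4, 120 × 0.875 = 105.
- Week 211 trough, Q1W: 255 × r/(1 − r). For h = 2 this is 616; for h = 4, 1348.
- Week 211 trough, Q2W: 510 × r²/(1 − r²). For h = 2 this is 510; for h = 4, 1231.
- Week 13 as a share of Week 211, Q1W: 39/616 = 6.4% (h = 2) and 105/1348 = 7.8% (h = 4).
- Week 13 as a share of Week 211, Q2W: 39/510 = 7.7% (h = 2) and 105/1231 = 8.5% (h = 4).

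The Week 13 sample is therefore at about 6–9% of the Week 211 trough. For comparison, Week 227 is 2^(−16/h) of Week 211: 0.4%, 2.5% and 6.3% for h = 2, 3 and 4. A low-concentration sample does exist, but after three doses at the lowest level rather than after full exposure.

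**The case against.** The strongest case against is that the gap is narrower than the blank cells suggest and the harm is unproven. Several stronger readings are tempting, and the documents do not support them.

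- **That no scheduled post-dose ADA sample is taken at low concentration.** The Week 13 sample is, and one positive sample is enough to class a baseline-negative participant as positive. It cannot detect a later response.
- **That off-drug ADA is never looked for.** Participants who stop treatment but stay in the study are asked to keep to the schedule (Sections 4.1.4 and 7.1), which has paired ADA and PK about every 26 weeks from Week 53. Unscheduled samples are also possible, including after hypersensitivity (A3–2). None of this gives completers a routine late sample.
- **That Section 8.8 contradicts the tables.** If the final visit means Early Termination, there is no conflict, because ADA is marked there. If it means the safety follow-up, Section 8.8 already asks for a late sample from discontinuers and the blank cell conflicts with it. The wording is ambiguous, and under either reading completers are not covered.
- **That ADA incidence is shown to be biased toward negative.** This depends on the assay's drug tolerance, which is not given. The protocol calls the immunogenic risk low (A3–3), reports no clinical findings indicative of an immunogenic response in about 2500 exposed participants (Section 2.3), and plans only descriptive summaries.
- **That the PK model lacks elimination-phase data.** The Q4W samples and those from participants off treatment inform elimination, and Section 9.4.5.3 allows data from other studies. The PK gain is secondary.

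One practical objection stands. Participants who continue gantenerumab after the study are not asked to attend Week 227 (Section 4.1.4), so pooling that sample into the main incidence would make detection depend on post-trial access.

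**Conclusion.** The point holds as a cheap improvement. Completers and early terminators are last sampled for ADA and PK 1–2 weeks after the last dose and have no scheduled sample after a long drug-free interval following full exposure. A visit 17–18 weeks after the last dose already draws their blood.

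The timing follows from the tables alone. The remaining-drug shares (50–87% against 0.2–9.5%) rest on an assumed half-life of 2–5 weeks and first-order decline. The risk that a masked or late response is classed as ADA-negative is real in principle, but its size cannot be computed from the documents. A reader should not conclude that the ADA endpoint is biased, or that Section 8.8 and the tables contradict each other.

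**What to change.** 1. Mark the ADA and PK rows in the follow-up column of Tables 2 and 5 (Week 227, or 15 weeks after Early Termination), using the draw already scheduled there.
2. State in Section 8.8 whether the final visit for participants who discontinue or withdraw is Early Termination, the safety follow-up, or both, and keep the tables in line with the answer.
3. In Section 9.4.5.4, keep post-baseline incidence through Week 211 or Early Termination as now. Report incidence including the follow-up sample separately, among those who attended, with the number attending.

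**Cost.** Two cells in each of two tables, one or two extra tubes at an existing draw, and one ADA and one PK assay per exposed attendee. Samples from participants never exposed to gantenerumab are generally not assayed (Section 6.3.2). No new visit or procedure is needed. The downside is incomplete attendance, which is why the late result is reported separately. The sample cannot be recovered for anyone who has already passed the follow-up visit.
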